There are limited data, however, on the use of systemic steroid treatment during periods of acute PEx in CF. IV steroid use has been reported predominantly in young infants with CF during episodes of respiratory illness and demonstrated modest improvements in flows as measured by functional residual capacity at follow up compared to the placebo group (38-39). Only one randomized, placebo controlled trial of oral prednisone in patients with CF has been published to date. The study by Dovey et al. randomized (in a 1:1 assignment, on the first day of antibiotic therapy) 24 CF patients age 10 years and older receiving IV antibiotics for a PEx to either oral prednisone 2 mg/kg/day divided twice daily for 5 days or placebo (13). The mean increase in FEV₁ % predicted in the prednisone vs placebo group was 12.2+5.2% vs 8.1+10.5% respectively, at day 6 and 14.7+8.8% vs 10.2+11.2% respectively, at day 14 of antibiotic therapy; these differences were not statistically significant. A limited number of subjects had sputum inflammatory markers assessed; in those that did, the mean change in sputum IL-8 from day 1 to day 14 of antibiotic therapy in the prednisone vs placebo group was $-0.2 \log_{10} \text{ pg/ml}$ (SD 0.7) vs $-0.5 \log_{10} \text{ pg/ml}$ (SD 0.3) which was not significantly different. In the subjects treated with prednisone, 6 developed glucosuria, two of whom also developed hyperglycemia. Two subjects

discontinued prednisone, one due to hypertension and one due to hyperglycemia. Based on the trend toward improvement in pulmonary function with prednisone therapy, the investigators calculated that 250 randomized subjects would be required to detect a 4% point difference in FEV₁ at day 14 of antibiotic treatment for a PEx. They concluded that the modest added benefit in lung function was not warranted given the side effects and lack of anti-inflammatory effect.

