The study by Dovey et al. has significant limitations in its design that affect its power calculations and conclusions about the value of future randomized controlled trials of steroid treatment in PExs. Firstly, the investigators randomized all patients presenting with an acute exacerbation. It is well known that 75% of these individuals will respond to traditional antibiotic treatment alone, diluting any potential beneficial effect of adjuvant steroid therapy. We propose to randomize subjects who have not recovered their baseline FEV₁ at day 7 of antibiotic treatment to prednisone, thereby maximizing any possible improvements while limiting exposure to adverse side effects. Additionally, Dovey et al. used the change in FEV₁ as a continuous primary outcome measure whereas we have shown that CF patients treated for a PEx clearly separate into responders and non-responders to antibiotic therapy at day 14 (**Figure 1**). It is therefore more appropriate to perform power calculations dichotomizing the primary outcome and using a test of proportions. Finally, the study by Dovey et al. had measurements of sputum inflammatory markers in a very limited number of patients and the study was thus not powered to detect significant changes in this outcome which is known to be widely variable between patients. Furthermore, the authors only measured sputum WBC count, IL-8 and leukotriene B₄ concentrations and not neutrophil elastase which is a more stable and predictive measure of airway inflammation in CF.

Therefore, oral steroid therapy has the potential to improve lung function in individuals in CF. Despite limited data, 17.5% of CF patients in the United States received one or more courses of oral corticosteroids in 1998 according to the Cystic Fibrosis Foundation Registry; many of these are given during acute pulmonary exacerbations. In a survey of adult CF physicians in the United Kingdom, 100% of respondents reported having used oral glucocorticoids as an adjuvant to IV antibiotic treatment during CF PExs (40). A well-designed randomized controlled trial of short-term oral steroid use during CF PExs in those who do not respond to IV antibiotic treatment is thus needed to inform clinical practice as to its potential efficacy. Our study proposes to fill this knowledge gap.

C. Research Design and Methods

Study design

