Patients will be randomized to receive either oral prednisone 2 mg/kg/day (max 60 mg; rounded to the nearest 10 mg) (Table 1) divided twice daily or oral placebo twice daily for 7 days in addition to the IV antibiotics prescribed by their physician (**Randomization**). On Day 7 only, it may be necessary on some occasions when the study drug (prednisone or placebo) is not available until the late afternoon, to give the study drug as one full dose (as opposed to twice daily). The choice and duration of antibiotic therapy will be left completely to the discretion of their treating physician. Study outcome measures will be obtained for all enrolled subjects at day 0 (± 2 days) and subsequently at day 7 (± 2 days), day 14 (± 2 days) of IV antibiotic treatment and at the 1 month follow up visit (approximately 1 month after day 14), as per usual standard of care (; **Table 2 Study Design Schedule**). However, day 0 may + 3 days when impacted by a Friday or long weekend admission/IV antibiotic start time. Patients who are receiving home IV antibiotic therapy for a PEx will also be eligible as they return to clinic weekly according to standard clinical care.

During the course of their admission, for patients willing to provide samples, the following specimens will be collected for the bio-repository for future analysis. All biological samples will be labeled using the patient's study number. The patient's study number will be linked to patient identifiers only by a master list that is managed by the PI and the Research Coordinator of this study:

- Sputum for inflammatory markers— For patients who can produce sputum, we will collect a research sputum sample which will be immediately sent on ice to collaborator [name] laboratory for processing for inflammatory markers and stored for future examination of biomarkers according to the standardized protocols developed by the Therapeutic Drug Network, US CF Foundation.

- Serum for biomarkers—Blood collection for future studies will occur at the time of clinical bloodwork or if a patient chooses to provide research blood separately. A total of 8 mls of blood will be drawn in two lavender top EDTA tubes in the phlebotomy clinic, stored on site and subsequently delivered to [name] laboratory at St. Paul's Hospital (a sub-site for the study) for final processing and storage.

Randomization and distribution of drug/placebo

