Subjects will be monitored for adverse events during hospitalization by the research coordinator and will be instructed to call the research coordinator with reports of adverse events once discharged. Adverse events will also be assessed at the 1 month follow up visit. Assessment of adverse events will include any mild events (transient event, no treatment change, e.g. cough), moderate events (treatment discontinued, e.g. hypertension, hyperglycemia) and severe events (gastrointestinal bleed, hospitalization or death). In the 1 year follow up, new infections with *P. aeruginosa*, *M. abscessus* or *B. cepacia* complex will be recorded in each group. Adverse events will be reported to the Research Ethics Board of each study site and to the study's Data Safety Monitoring Board (DSMB). Withdrawals from the study and the reason for it will also be recorded as an outcome measure.

vii) The change in the measurement of sputum (neutrophil count, neutrophil elastase and IL-8 levels) and serum (including neutrophil count and hsCRP) inflammatory markers measured at day 0, day 7, day 14 of IV antibiotic treatment and the 1 month follow up visit in each treatment arm.

The anti-inflammatory effects of steroid therapy will be examined in both the lung and serum. Sputum will be collected at all study sites and immediately shipped on ice to collaborator [name] laboratory for processing as previously described according the standardized protocols developed by the Therapeutic Drug Network, US CF Foundation (48). Serum samples will also be collected at these time points for neutrophil count and CRP measurements through the hospital laboratory as part of clinical care and an aliquot will be banked for future serum biomarker studies at each study site (49-50).

F. Sample size calculation

To calculate the sample size for the primary outcome, we did an analysis using the Toronto CF Database of all the PExs treated with IV antibiotics from 1997-2012 at the Hospital for Sick Children and St Michael's Hospital (almost 3,000 PEx). When examining PExs for which all

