When target sample size is reached, the study statistician (who will not be involved in the conduct of the study) will unblind the treatment allocation (identify who is in group A vs B but not identify the groups themselves as active drug or placebo) and estimate the treatment effect between the two groups based on the primary outcome (intention-to-treat). If there is a statistically significant treatment effect ($p<0.05$), the study statistician will do the following statistical analyses. For the primary outcome we will compare the proportion of randomized patients that responded at day 14 of therapy in the placebo arm compared with the treatment arm using a two sample test for proportions. We will perform intent-to-treat analysis according to the treatment arm subjects were randomized to. We will also perform a per-protocol analysis based on subjects who completed the 7 days of prednisone or placebo as per protocol. The same analysis will be performed for the proportion responding to therapy at 1 month. Logistic regression analysis will then be performed to adjust for potential confounders, such as age, gender, *Pseudomonas aeruginosa* or methicillin-resistant *Staphylococcus aureus* (MRSA) infection and lower FEV₁, as these factors have been associated with failure to recover lung function after an exacerbation (3, 25). For the additional secondary outcomes, absolute change in pulmonary function tests, length of hospitalizations and change in sputum measurements,

we will use parametric (t-test), or non-parametric (Mann-Whitney) two sample comparison test. Linear regression analysis will be then performed to adjust for potential confounders, as listed above. Time to subsequent exacerbation will be compared using a Cox proportional hazard model. Potential confounders will be adjusted for in the Cox-proportional hazard model. All secondary outcomes will be analyzed both as intention-to-treat and per-protocol. All outcomes will be obtained for all subjects irrespective of whether they completed the study per protocol. In the case of missing data, we will perform the analysis on complete (complete case analysis). To determine whether diabetic patients have a different response compared to non-diabetic patients, we will perform a sensitivity analysis comparing return to baseline lung function in diabetics vs non-diabetics according to treatment group.

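### No scale is set for the sputum markers, and on untransformed change the planned tests lose power that a log10 analysis would keep

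*Combined protocol and SAP*

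**What the plan says.** Section E, secondary outcome vii, is "The change in the measurement of sputum (neutrophil count, neutrophil elastase and IL-8 levels", together with serum markers, at day 0, day 7, day 14 and the 1 month visit. It does not say whether change is a difference, a ratio or a log difference, nor from which visit it is counted.

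Section G lists the outcomes for two-sample testing as "absolute change in pulmonary function tests, length of hospitalizations and change in sputum measurements" and gives the method: "we will use parametric (t-test), or non-parametric (Mann-Whitney) two sample comparison test". There is no rule for choosing between the two tests. It then says: "Linear regression analysis will be then performed to adjust for potential confounders, as listed above". The confounders listed are age, gender, *P. aeruginosa* or MRSA "infection and lower FEV₁, as these factors have been associated with failure to recover lung function after an exacerbation". The marker's own starting value is not among them.

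Section B, item 2, reports the earlier randomized trial's IL-8 change from day 1 to day 14 on the log10 scale: -0.2 (SD 0.7) on prednisone and -0.5 (SD 0.3) on placebo. The same section faults that trial for lacking power on "this outcome which is known to be widely variable between patients".

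Not every patient contributes. Section D says "For patients who can produce sputum, we will collect a research sputum sample".

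**The concern.** Suppressing excess lung inflammation is the hypothesis stated at the start of the protocol, and the sputum markers are where it is tested in the lung. The background treats IL-8 as a quantity that varies by multiples, but the analysis section does not carry that scale over.

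On the raw scale, a given proportional effect produces a change proportional to where the patient started. A halving is a fall of 5 units from 10 and of 50 units from 100. With a between-patient log10 SD of 0.4, two SDs either side of the median span 10^1.6, about 40-fold; with 0.6 they span 10^2.4, about 250-fold. Raw differences therefore mostly reflect starting level. That inflates the variance in a t-test or linear regression, and it blurs the ranks in Mann-Whitney.

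The stake is power on a mechanistic outcome whose numbers are already limited by who can produce sputum. If the scale stays open, scale and test can also be chosen after the data are seen.

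**Working it through.** **The plan's own figure.** Only the primary outcome is powered. For 30% against 60%, two-sided 5%, 80% power and pooled variance: n = [1.96·√(2·0.45·0.55) + 0.842·√(0.3·0.7 + 0.6·0.4)]² / 0.30² = (1.379 + 0.565)² / 0.09 ≈ 42 per arm. This matches section F. The sputum markers have no power statement, so everything below rests partly on assumptions.

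**Inputs from the documents.** SDs of log10 IL-8 change 0.7 and 0.3, weighted equally because the numbers with sputum are not given: √((0.49 + 0.09)/2) = 0.54.

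**Assumptions.**
- 30 sputum producers per arm (20 and 42 also tried).
- Between-patient log10 SD at the start of 0.4 or 0.6.
- True extra reduction two-fold, log10(2) = 0.30.
- Fall common to both arms of 0 or 0.35 log10. The 0.35 is the midpoint of the earlier trial's 0.2 and 0.5 over day 1 to day 14. This trial randomizes at day 7, and no fall or SD is given for day 7 to day 14, so zero is the other bound.

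**Model.** Log10 start ~ N(0, s); log10 change ~ N(-fall, 0.54), with a further -0.30 in one arm; raw change = 10^(start + change) - 10^start. Two-sided 5%. With 2,500 trials per setting the standard error is at most √(0.25/2,500) = 1 percentage point.

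**Direct check of the log10 t-test.** 0.30 / (0.54·√(2/30)) = 2.15, which against a critical value of about 2.00 gives power of about 56%.

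**Power, two-fold effect:**

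| Per arm | Common fall | Start SD | Raw t-test | Raw Mann-Whitney | Log10 t-test |
|---|---|---|---|---|---|
| 30 | 0.35 | 0.4 | 19% | 28% | 57% |
| 30 | 0.35 | 0.6 | 11% | 24% | 57% |
| 30 | 0 | 0.4-0.6 | 16-23% | 38-41% | 55-57% |
| 42 | 0.35 | 0.4 | 25% | 39% | 71% |
| 42 | 0.35 | 0.6 | 15% | 34% | 73% |
| 20 | 0.35 | 0.4 | 12% | 20% | 40% |
| 20 | 0.35 | 0.6 | 8% | 18% | 41% |

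Repeat runs differ by one or two points.

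**Second model, same SD at each visit.** With 42 per arm, visit SD 0.6, change SD 0.54, flat placebo and a two-fold effect: raw t-test 23%, raw Mann-Whitney 49%, log10 t-test 71%, log10 regression with starting value 80%. With a placebo fall of 0.25 log10: 12%, 31%, 71%, 80%. Across this model's scenarios the three most extreme of 84 patients carry about 47-83% of the raw-change variance.

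**Starting value as covariate.** In the second model with 30 per arm, visit SD 0.4 and placebo fall 0.25, the log10 t-test has 57%. Raw regression with the starting value has 66%, and log10 regression with it has 82%. The covariate the plan omits can matter as much as the scale.

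**Type I error.** 2-5% in the null runs, so the cost is power, not false positives.

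**The case against.** A reader might infer that the plan has chosen raw change. It has not said so: section G attaches the word absolute to lung function only, and a t-test on log10 change would fit its wording. The authors plainly know the log scale, since they quote it. This stands. A simple difference is the default reading, not a stated decision.

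A reader might also infer that a few high values decide all three analyses. For Mann-Whitney that is wrong, because ranks bound the influence of extremes. Offering a rank test is a conventional provision for skewed data. What remains is a power loss of a different kind, from ranking raw differences that still depend on starting level. It shrinks to 38-41% against 55-57% when there is no common fall.

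The inputs are also open to challenge. The SD comes from the earlier trial's day 1 to day 14 window. The two-fold benefit has no support in that trial, where IL-8 fell less on prednisone. The IL-8 spread is applied to all three markers, although section B describes elastase as the more stable one. These points limit how far the size can be trusted. They do not reverse the direction: with the tests as listed, the log10 scale had more power in every setting tried.

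Finally, this is an unpowered secondary outcome, and the primary result is untouched.

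**Conclusion.** The concern holds as a gap in specification with a real cost in power. Section G fixes neither the scale, nor the rule for choosing the test, nor the starting value as covariate. If it is read as a simple difference, power for a two-fold effect at 30 per arm is roughly 11-23% (t-test) or 23-41% (Mann-Whitney), against 55-57% for a log10 t-test. These figures depend on the assumed spread, effect, common fall and number of sputum producers.

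The documents do not support the further inference that a true anti-inflammatory effect would probably be missed. They give none of those four inputs for this trial. With a 3.2-fold effect (0.5 log10), raw Mann-Whitney reaches 75-79% at 30 per arm with no common fall, and 82% in the second model at 42 per arm with flat placebo. Conversely, at 20 per arm the log10 t-test has only about 40% power for a two-fold effect, so scale is not the only limit.

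**What to change.** In section G, prespecify that sputum neutrophil count, elastase and IL-8, and serum CRP, are analysed as log10 values in both the two-sample test and the regression. The log10 day 7 (pre-randomization) value should preferably be a covariate in the regression. Report treatment effects as ratios of geometric means with confidence intervals, and show by arm how many patients gave sputum.

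This takes a sentence or two and needs no new data or patients. The one downside is that values at or below the assay limit cannot be logged as they stand. A substitution rule has to be written down before unblinding.

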The questionnaire that will be used is the Cystic Fibrosis Questionnaire-Revised (CFQ-R) Respiratory domain (44). The CFQ-R is a disease-specific instrument that measures health-related quality of life for adolescents and adults with CF with a developmentally appropriate version for children. The CFQ-R is a reliable and valid measure of quality of life for individuals with CF and is frequently used in clinical trials to assess the effects of new therapies (45). In addition, subjects will also be asked to complete the CF Respiratory Symptom Diary (CFRSD) on day 0, day 7, day 14 and at the 1 month follow up visit(46). The Chronic Respiratory Infection Symptom Score will be applied to the CFRSD to calculate a severity score from 0-100 (100 being most severe). The CRISS score has been previously shown to be a responsive measure of steroid treatment effect in CF pulmonary exacerbations(47).

iv)The length of hospitalization and duration of IV antibiotic treatment in each treatment arm.

Length of hospitalization (number of days in hospital) and duration of IV antibiotic treatment are clinically relevant and patient-meaningful outcomes that will be calculated for each patient and compared between treatment groups.

v) The time to subsequent PEx in each treatment arm.

Based on our previous study, we know that the time between exacerbations is one of the most important determinants of overall lung function decline in an individual with CF (6). Time to subsequent pulmonary exacerbation will be calculated from the last day of IV antibiotic therapy of the randomized exacerbation to the first day of re-starting IV antibiotic treatment for a new pulmonary exacerbation (minimum 21 days between events). We will compare the average (or median if data not normally distributed) duration between treatment groups. We will follow up patients for subsequent exacerbations for 1 year following their randomized exacerbation.

vi) The number of adverse events and withdrawals from study recorded in each treatment arm.

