height using the NIH guidelines(56)) and will monitor for these adverse events (see below-Safety Monitoring Plan). In addition, all untoward medical occurrences, whether or not deemed causally related to study participation, will be recorded and site investigators will be asked to assess both severity and whether or not the adverse event was related to study participation. We will use the following grading scale to assess adverse events:

Adverse Event Category	Description
Mild	transient event, no treatment change, e.g. glucosuria
Moderate	treatment discontinued e.g. severe/sustained hypertension or hyperglycemia
Severe	severe: death, unexpected hospitalization

Given that subjects will be randomized at the time of hospitalization for a pulmonary exacerbation, we will monitor the time to subsequent exacerbation. If we observe a shorter time to subsequent exacerbation in one of the treatment arms, this will be reported to the DSMB.

Reporting of AEs

All adverse events will be recorded by the research coordinator and reported to the study site investigator as well as the PI ([name]), who will oversee close and continuous monitoring for safety concerns throughout the trial. All serious adverse events will be reported to Health Canada, based on the Health Canada Guidance: Adverse Drug Reactions (ADRs) Reporting Criteria. All serious and unexpected adverse events will also be reported to the REB at each study site as well the REB at the Hospital for Sick Children (as study sponsor) within 48 hours of their occurrence. Adverse events will also be reported to the Data Safety Monitoring Board (DSMB) (see below) in the form of regular reports submitted every 6 months. Serious adverse events will be reported to the DSMB within 48 hours.

Safety Monitoring Plan

Hospitalized subjects will be monitored on day 7, day 10 (+/- 2 days) and on day 14 with urine dip glucose measurements while on prednisone (or placebo). If the urine glucose is > 2+, a serum glucose measurement will be performed. All the information will be provided to the treating physicians; they can decide at any time to withdraw their patient and request unblinding of the treatment allocation. To unblind a subject, the research coordinator or physician will call the PI ([name]) at [contact] [name] or page [contact]

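### The per-protocol analysis of adverse events and withdrawals excludes, by definition, patients whose study drug was stopped early, so it cannot show the harms that ended treatment

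*Combined protocol and SAP*

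**What the plan says.** Section E lists as secondary outcome vi: "The number of adverse events and withdrawals from study recorded in each treatment arm". Under that heading it adds: "Withdrawals from the study and the reason for it will also be recorded as an outcome measure". It describes the middle grade of adverse event as "moderate events (treatment discontinued, e.g. hypertension, hyperglycemia". The grading table in Appendix 1.2 defines the same grade as "treatment discontinued e.g. severe/sustained hypertension or hyperglycemia".

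Section G sets out the analysis populations. The primary analysis is intention-to-treat by randomised arm, and then: "We will also perform a per-protocol analysis based on subjects who completed the 7 days of prednisone or placebo as per protocol". For the secondary outcomes it states: "All secondary outcomes will be analyzed both as intention-to-treat and per-protocol". It makes no exception for outcome vi, and neither the protocol nor its appendices define a separate safety set.

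Section G also says: "All outcomes will be obtained for all subjects irrespective of whether they completed the study per protocol".

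**The concern.** Completing the course is something that happens after randomisation and can depend on the drug. Appendix 1.2 names hyperglycemia, glucosuria and hypertension as the events most expected. It leaves withdrawal for hypertension or hyperglycemia to the treating physician, and it provides for diabetic patients to be discontinued if their glucose control cannot be managed. A set restricted to completers therefore drops patients because of the drug's anticipated effects.

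For efficacy this is the usual limitation of a per-protocol analysis. For outcome vi it is more serious, because being stopped early is itself part of what is being counted. The plan would then contain two pre-specified safety comparisons with no stated ranking, one of which cannot show early stops. Section K ties the case for taking prednisone into practice to better recovery without an excess of adverse effects, and it does not say which analysis of harms is meant.

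**Working it through.** **The plan's own figure.** Section F gives 42 per arm for 30% v 60%, 80% power and 5% significance (two-sided assumed). The usual two-proportion formula gives

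n = [1.96 × √(2 × 0.45 × 0.55) + 0.842 × √(0.3 × 0.7 + 0.6 × 0.4)]² / 0.30² = (1.379 + 0.565)² / 0.09 ≈ 42.

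The figure reproduces, and nothing below changes it. The plan gives no figure for the safety analysis or for the size of the per-protocol set.

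**Step 1: definitions side by side.**
- The per-protocol set is "subjects who completed the 7 days of prednisone or placebo as per protocol".
- A patient whose study drug was stopped before the end of the 7 days is not in that set.
- So, within the set, adverse events that stopped study drug = 0 and withdrawals during dosing = 0, in both arms. The difference between arms is 0 whatever the true difference is. This follows from the definitions and needs no assumed rate.

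**Step 2: scale.** Section B (item 2) and Appendix 1.2 report that, in the pilot trial of prednisone, 2 of 12 prednisone subjects stopped, one for hypertension and one for hyperglycemia.
- Rate: 2/12 = 16.7%; exact (Clopper-Pearson) 95% CI 2.1% to 48.4%.
- Applied to 42 patients: 42 × 2/12 = 7.0; limits 42 × 0.021 = 0.9 and 42 × 0.484 = 20.3.
- The completer set on prednisone would then be 42 − 7 = 35.
- The trial's own rate is unknown. At assumed rates of 5%, 10% and 20%, the patients removed are 2.1, 4.2 and 8.4 of 42.

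**Step 3: effect on the other harm counts.** Re-cut the pilot to completers. Prednisone goes from 12 to 10; placebo is assumed to stay at 12, because no placebo stop is reported.

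| Event | All subjects, prednisone v placebo | Completers only |
|---|---|---|
| Stopped drug for an adverse event | 2/12 v 0/12 (placebo assumed) | 0/10 v 0/12 |
| Hypertension | 2/12 v 2/12 (difference 0) | 1/10 v 2/12 (10.0% − 16.7% = −6.7 points) |
| Hyperglycemia, prednisone arm only | 2/12 (16.7%) | 1/10 (10.0%) |
| Glucosuria | 6/12 v 1/12 | 4/10 or 5/10 v 1/12 |

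The hypertension and hyperglycemia rows assume that neither withdrawn subject was also the other case of the other event. If one was, that completer count falls to 0/10. The glucosuria row has two values because the subject withdrawn for hyperglycemia had glucosuria, while the status of the subject withdrawn for hypertension is not given.

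The distortion is thus total for events that stop the drug and partial for hypertension and hyperglycemia. It is small for glucosuria, which did not in itself lead to stopping.

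**The case against.** The strongest reply is that the plan already protects the safety data. The sentence that brings in the per-protocol analysis also requires intention-to-treat. Outcomes are to be obtained on everyone, Appendix 1.2 records all untoward events with severity and relatedness, and the safety board's reports and mid-way analysis are not described as limited to completers. All of this stands. A reader might infer that the trial will lose its drug-stopping harms, but the documents do not support that.

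A reader might also infer that the tolerability conclusion in Section K rests on the completer set. It does not. That passage speaks of the subjects treated in the trial, is not a decision rule, and names no analysis set.

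Nor is the per-protocol safety table empty. Mild events, severe events in completers, one-year new infections and withdrawals after dosing all remain in it. The moderate grade refers to treatment being discontinued, so a moderate event arising after the 7 days is not excluded by definition either.

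Finally, Section G names no test for outcome vi, so the blanket sentence may be loose drafting. That is plausible, but as written it includes safety. These points limit the consequence; they do not remove the defect.

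**Conclusion.** The concern holds for the per-protocol analysis of outcome vi and no further. In that analysis, early stops of study drug and the adverse events that caused them are zero in both arms by construction, and counts of hyperglycemia and hypertension are reduced. For drug-stopping events the contrast is forced to no difference. For the others the direction depends on which arm has more stops. If that is prednisone, as in the pilot, any excess on prednisone is understated, and in the pilot's hypertension counts the comparison even tips in its favour.

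The figure of about 7 of 42 (about 1 to 20) is illustrative. It carries a rate based on 12 patients given a 5-day course from the start of antibiotics over to a 7-day course in patients not recovered at day 7. It measures what would be missing from the per-protocol set, not what the trial would lose, since the intention-to-treat analysis would count the same patients. The structural zero does not depend on it.

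This is a modest point that should be corrected because a biased safety comparison should not be pre-specified. It does not affect the sample size or the primary analysis.

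**What to change.** In Section G, replace the blanket sentence with wording to this effect: the per-protocol analysis applies to the primary outcome and to secondary outcomes i to v and vii; outcome vi is analysed in all randomised patients by assigned arm, counting events whether or not the course was completed; early stopping of study drug, with reasons, is reported by arm in the same patients.

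An analysis of adverse events in patients who took at least one dose, by drug actually received, may be added as support. It should not replace the analysis of all randomised patients for withdrawals, because a patient who withdraws between randomisation and first dose would then disappear from the count.

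The cost is a sentence or two of text and the loss of one uninformative supplementary table. No new data, visits or patients are needed, and the target of 84 is unchanged. The change is best made before the allocation is opened for analysis, so that it cannot appear to be driven by the results.
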